## 8.6 Analyses

### 8.6.1 Primary Analysis

#### 8.6.1.1 Safety

Each participant's safety data will be summarized as: the worst grade of adverse event experienced during the time period of observation for primary objectives and the worst grade of adverse event judged to be at least possibly related to the immunization(s) during the same time interval. Descriptive analyses will consist of frequency distributions of these safety outcomes, broken down by dose group/Cohort. All available safety data will be used. All infants who receive an initial VRC01, VRC01LS, or VRC07-523LS immunization will be included in all analyses regardless of whether they receive ARV prophylaxis or are HIV-infected.

With the small sample size used in this study, there will be insufficient statistical power for a formal test of differences between dose groups with respect to safety. With insufficient power, a finding of no significant difference would not provide acceptable evidence of no adverse dose effect. Thus, estimates of Grade 3 or higher toxicity rates will be computed separately for each dose group and bounded by 90% confidence intervals (CI), reflecting the precision of the estimates. This will provide 95% assurance that the true rate of severe adverse events is not higher than the upper limits of the CI around the proportion of participants with grade 3 or higher events in the study sample. Because of the small sample sizes and the anticipated low toxicity rates, these intervals will be calculated using exact methods.

#### 8.6.1.2 Precision of Estimates

The following table (Table 7) illustrates the confidence intervals for a range of hypothetical proportions of adverse events. This table shows that a sample finding of no grade 3 or higher adverse events in a total sample of 10 participants would provide 95% confidence that the probability in the population from which the sample was drawn is no greater than 26%.

**Table 7: Exact 90% Confidence Intervals around Potential Proportions of Participants Exhibiting Grade 3 or Higher Adverse Events (N=8, 10 and 13)**

Sample Toxicity Rates	90% Confidence Limits	
	Lower	Upper
0% (0/8)	0%	31%
12.5% (1/8)	0.6%	47%
25% (2/8)	5%	60%
37.5% (3/8)	11%	71%
50% (4/8)	19%	81%
0% (0/10)	0%	26%
10% (1/10)	0.5%	40%
20% (2/10)	4%	51%
30% (3/10)	9%	61%
40% (4/10)	15%	70%
0% (0/13)	0%	21%
7.7% (1/13)	0.4%	32%
15.4% (2/13)	3%	41%
23.1% (3/13)	7%	49%
30.8% (4/13)	11%	57%

The proportions of infants in each dose group with adequate PK levels (see Section 9 for definition) and other PK results will be presented in a separate PK report, The table below (Table 8) presents exact 90% confidence intervals around various potential rates of PK success which might be observed in a total sample of 10 participants. This table shows that a sample finding of PK success in 6 of 10 participants would provide 95% confidence that the rate in the population from which the sample was drawn is no lower than 30%.

**Table 8: Exact 90% Confidence Intervals around Potential Rates of PK Success (N=8, 10 and 13)**

Sample Rates of PK Success	90% Confidence Limits	
	Lower	Upper
62.5% (5/8)	29%	89%
75% (6/8)	40%	95%
87.5% (7/8)	53%	99%
100% (8/8)	69%	100%
50% (5/10)	22%	78%
60% (6/10)	30%	85%
70% (7/10)	39%	91%
80% (8/10)	49%	96%
90% (9/10)	61%	99.5%
100% (10/10)	74%	100%
38.5% (5/13)	17%	65%
46.2% (6/13)	22%	71%
53.8% (7/13)	29%	78%
61.5% (8/13)	35%	83%
69.2% (9/13)	43%	89%
76.9% (10/13)	51%	93%
84.6% (11/13)	59%	97%
92.3% (12/13)	68%	99.6%
100% (13/13)	79%	100%

Should this occur, the number of infants in each dose group who become HIV-infected will be reported. The immunization is not expected to increase the rate of HIV infection. However, since these infants are born to women at increased risk of intrapartum HIV transmission, it is possible that a small percentage might become HIV-infected, and any infections will be brought to the attention of the SMC.

## 8.7 Secondary Analyses

Adverse events occurring after the initial review period and throughout the remainder of follow-up will be summarized in the same way as for the primary safety objective.

The number of infants in each dose group who develop anti-VRC01, VRC01LS, or VRC07-523LS antibodies will be summarized descriptively.

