## **6 PARTICIPANT MANAGEMENT**

### **6.1 Toxicity Management**

The DAIDS Table for Grading the Severity of Adult and Pediatric Adverse Events, (DAIDS AE Grading Table), Corrected Version 2.1, July 2017, must be used and is available on the RSC website at <https://rsc.niaid.nih.gov/clinical-research-sites/daims-adverse-event-grading-tables>

Management of adverse experiences is done according to the best clinical practice and the judgment of the site investigator. Alternate explanations for clinical and laboratory abnormalities must be sought. Laboratory normals will be the institutional values. However, if a site does not have an age-specific normal range/value for a particular lab, the site should use the latest edition of the Harriet Lane Handbook for normal ranges/values and document this for

monitoring purposes. Abnormal clinical and laboratory findings should be followed until resolution to < Grade 2, or no further change expected.

This study involves a single or multiple dose(s) of VRC01, VRC01LS, or VRC07-523LS antibody. Safety data will be collected and reviewed by the study team on regular (twice a month) study conference calls.

Sites record and submit CRFs to the Data Management Center on all AEs from the time of the initial immunization as follows:

For Dose Groups 4 and 5 (both cohorts), all laboratory events required by the Schedules of Evaluations should be recorded on CRFs regardless of grade. See the CRF instructions for further details. For all other events:

- For Grade 1 reactogenicity AEs, and all Grade 2 AEs that study sites assess as possibly, probably or definitely related to the study product, and all AEs grade 3 or higher (regardless of their relationship to study product): CRFs should be submitted through the entire course of study.
- For all Grade 1 AEs (other than reactogenicity AEs), and Grade 2 AEs that sites assess as definitely not or probably not related to the study product: CRFs should only be submitted for these AEs occurring up to 30 days after the single immunization for Dose Groups 1 and 2 and Dose Groups 4 and 5 (Cohort 1) or 30 days after the final immunization for Dose Group 3 and Dose Groups 4 and 5 (Cohort 2). After that, sites will not be required to record/submit these AEs on CRFs. Note that sites should continue to report – beyond the time periods specified above – unresolved AEs that began during the reporting period.

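### Section 8.7 carries an all-grade worst-grade table into later follow-up, where Section 6.1 no longer requires new non-reactogenicity Grade 1 or unrelated Grade 2 events to be recorded

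*Protocol*

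**What the plan says.** **Summary.** Protocol Section 8.6.1.1 reduces each infant's safety data to "the worst grade of adverse event experienced during the time period of observation for primary objectives" and the worst grade judged at least possibly related. It reports both as frequency distributions by dose group and cohort. Section 8.7 then states that events after the initial review period and "throughout the remainder of follow-up will be summarized in the same way as for the primary safety objective". Neither section sets a lower limit on grade.

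**Collection.** Protocol Section 6.1 sorts events by type.
- "For all Grade 1 AEs (other than reactogenicity AEs), and Grade 2 AEs that sites assess as definitely not or probably not related" to the product: "CRFs should only be submitted for these AEs occurring up to 30 days after the single immunization for Dose Groups 1 and 2". The same limit applies to Cohort 1 of Dose Groups 4 and 5. In Dose Group 3 and in Cohort 2 of Dose Groups 4 and 5, the 30 days run from the final dose. "After that, sites will not be required to record/submit these AEs on CRFs".
- "For Grade 1 reactogenicity AEs, and all Grade 2 AEs that study sites assess as possibly, probably or definitely related to the study product", and every event of Grade 3 or higher: collected for the whole study.
- Dose Groups 4 and 5 only: "all laboratory events required by the Schedules of Evaluations should be recorded on CRFs regardless of grade".
- Events that began inside the reporting period and have not resolved continue to be reported.

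**Listed outcomes.** Protocol Sections 8.2.1.1 and 8.2.2, SAP Sections 3.1 and 3.2, and SAP Section 5 (items 7 and 8) list death, Grade 3 or higher events, related Grade 3 or higher events, and HIV infection. SAP Sections 1.1 and 5 leave table detail to the Analysis Implementation Plan (AIP), which is not among the documents reviewed.

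**The concern.** A worst-grade distribution is meaningful below Grade 3 only while those grades are being recorded. After the cut-off, an infant whose only new clinical events are of the restricted types falls into a lower cell, usually 'no event'. The later table would then show less mild toxicity than the primary table even if nothing had changed in the infants. The worst related grade is affected too, because non-reactogenicity Grade 1 events stop being collected whatever their attribution.

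The study is Phase 1, in newborns, and has no control arm. A reader who sets the two periods side by side could take the drop for waning toxicity. Groups also differ in what is kept: Section 6.1 states the any-grade laboratory rule for Dose Groups 4 and 5 only.

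In Cohort 2 the cut-off follows the final dose, so an infant who gets only the birth dose may lose this collection inside the Week 16 primary window. Missing the second dose is not random. It can follow toxicity (Section 6.1.1), a negative maternal confirmatory test (6.2), HIV infection (6.6) or weaning.

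**Working it through.** **Plan's own figures.** The documents give no figure for Grade 1-2 events. The nearest safety figures are the zero-event upper limits in Table 7, 1 − 0.05^(1/n): 31.2% for n=8, 25.9% for n=10 and 20.6% for n=13, against 31%, 26% and 21% printed. They concern Grade 3 or higher events, which are collected throughout, so this point does not change them.

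**Inputs**, as nominal days from first dose:
- Primary window end P: Day 28, Week 16 = Day 112, or Week 24 = Day 168 (Section 8.2.1.1).
- End of follow-up E: Week 48 = Day 336 (Dose Groups 1-2) or Week 96 = Day 672 (Dose Groups 3-5).
- Collection end C = last-dose day + 30 (Section 6.1). Last-dose day is 0 for one dose, 84 for a Week 12 dose, and 168 to 504 in Dose Group 3. The Schema says that all Dose Group 3 infants received monthly doses for at least 6 months.

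**Share of the later window covered** = max(0, min(C, E) − P) / (E − P):

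| Group | C | P to E | Covered |
|---|---|---|---|
| Dose Groups 1-2 | 30 | 28 to 336 | 2/308 = 0.6% |
| Dose Groups 4-5, Cohort 1 | 30 | 28 to 672 | 2/644 = 0.3% |
| Dose Groups 4-5, Cohort 2, two doses | 84 + 30 = 114 | 112 to 672 | 2/560 = 0.4% |
| Dose Groups 4-5, Cohort 2, one dose | 30 | 112 to 672 | 0/560 = 0% |
| Dose Group 3, last dose Week 24 | 168 + 30 = 198 | 168 to 672 | 30/504 = 6.0% |
| Dose Group 3, last dose Week 72 | 504 + 30 = 534 | 168 to 672 | 366/504 = 72.6% |

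**Share of the primary window covered** = min(C, P) / P. This is 100% in every row except one-dose Cohort 2. There the literal rule gives 30/112 = 26.8%. If a site keeps collecting until the Week 12 dosing decision, it is 84/112 = 75%.

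**Illustration, Dose Groups 1-2.** Assume a constant probability p per 28 days of at least one restricted event. The documents give no such rate, so a range is shown. The primary window records p. The later window records 1 − (1 − p)^(2/28), against a true 1 − (1 − p)^(308/28).
- p = 10%: 10% in the primary window; later 1% recorded, 69% true.
- p = 30%: 30% in the primary window; later 3% recorded, 98% true.
- p = 50%: 50% in the primary window; later 5% recorded, nearly 100% true.

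In Dose Group 3 dosed to Week 72, p = 30% gives 99% recorded against nearly 100% true, so there is almost no artificial fall.

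**The case against.** The best defence is that the SAP already confines the later-period report to the right events. Item 8 of its Section 5 lists death, Grade 3 or higher, related Grade 3 or higher, and HIV infection, with exact 90% intervals, and has no Grade 1-2 row. Grade 3 or higher events are collected for the whole study. No early-versus-late or one-dose-versus-two-dose comparison is planned, the distributions are descriptive, and the AIP may carry a footnote that cannot be seen here.

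Most of this stands. A reader might infer that the trial's reported safety proportions are biased; the documents do not support that. A reader might also infer that all mild events stop being collected 30 days after any dose. They do not: the clock runs from the final dose, and Grade 1 reactogenicity, related Grade 2 events, unresolved events and scheduled laboratory events in Dose Groups 4-5 all continue. Nor is 27% primary-window coverage an established fact for one-dose Cohort 2 infants. At Day 30 a site usually cannot know that the birth dose was final, so about 75% is more plausible unless a second dose has already been ruled out. The number of such infants is not given, and Cohort 2 entry requires that the mother intends to breastfeed.

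What the defence does not remove is the protocol text. Sections 8.6.1.1 and 8.7 still promise the all-grade table, and the SAP neither lists nor withdraws it. Either it is produced with the shift built in, or a protocol-specified analysis disappears without comment.

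**Conclusion.** The point holds for one item: the later-period worst-grade distribution that Section 8.7 takes over from 8.6.1.1. Followed as written, that distribution is shifted downward below Grade 3 in Dose Groups 1-2 and 4-5, where 0% to 0.6% of the later window is covered. In Dose Groups 4-5 this applies to events other than scheduled laboratory events. In Dose Group 3 the shift varies, with coverage from 6% to 73%. The worst related grade is affected only at Grade 1.

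The listed outcomes and their exact 90% intervals stand, as do sample size and precision. Within the primary window, the only gap is in one-dose Cohort 2 infants, at 27% to 75% coverage depending on how sites apply the rule. With 10 infants planned per cohort, each such infant is 10 percentage points of the table.

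The coverage figures rest on nominal visit days and on sites stopping when they are permitted to. The illustrated event rates are assumptions.

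**What to change.** In Section 8.7 and the table shells, replace the instruction to summarise in the same way with two later-period distributions limited to grades collected throughout:
- all-cause worst grade: 'no Grade ≥3 event', 3, 4, 5;
- worst related grade: 'no related Grade ≥2 event', 2, 3, 4, 5.

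Report in separate tables the lower-grade events collected in Dose Group 3 up to 30 days after the final dose, and the scheduled laboratory events of any grade in Dose Groups 4-5, so that collected data are not discarded.

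For Cohort 2, keep the Week 16 primary window, but show the all-grade distribution by number of doses received and state when collection of lower grades ended.

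The cost is wording, shells and a few extra descriptive tables. No new data are needed, and no sample size or confidence interval changes.

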## 8.8 Exploratory Analyses

The VRC01, VRC01LS, and VRC07-523LS antibody levels in oral secretions will be summarized at each time point by calculating 95% CI around the mean or median, depending on whether the data are normally distributed.

Exploratory analyses will be performed in the infants who are determined to be HIV-infected. The neutralization sensitivity of the infant and maternal virus will be documented descriptively. In addition, the changes from baseline to subsequent time points in the amount of HIV provirus in PBMC and plasma HIV-1 RNA (measured in copies/mL) over time will be presented. HIV serum neutralization titer before and after the study immunization will be compared.

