VRC 601 demonstrated antiviral effect. A single 40 mg/kg IV dose led to a 1.1 to 1.8- $\log_{10}$  drop in plasma viral load in 6 of the 8 viremic participants not on ART [33]. Two viremic participants had only a marginal drop in plasma viral loads of 0.26 and 0.18  $\log_{10}$  copies/mL, respectively; however, these two individuals were found to have baseline virus that was relatively neutralization resistant. Two adults, who had baseline plasma viremia <1000 copies/mL, had sustained suppression of viremia for over 20 days, until the plasma level of VRC01 decreased. The adults with higher baseline plasma viremia had evidence of outgrowth of escape variants in rebound viremia. These data indicate that a single dose of VRC01 at 40 mg/kg IV given as monotherapy resulted in an average virus load significantly decreased between days 3 and 21 after infusion compared to baseline, with the nadir at day 9. A 0.5  $\log_{10}$  copies/mL or greater decrease in plasma viral load is considered a positive antiviral response to a single antiretroviral drug. Among the ART-treated, virally suppressed adults, no change in proviral DNA load was observed after receiving two infusions of VRC01. However, the study demonstrated a VRC01-mediated anti-viral effect, with preferential suppression of neutralization-sensitive strains [33].

VRC 602 was the first study of the VRC01 mAb in HIV-1-uninfected adults [34]. It was a dose-escalation study to examine safety, tolerability, dose, and PK of VRC01. VRC 602 opened in December 2013 as a single-site study at the NIH Clinical Center, Bethesda, Maryland, and the final infusion was administered in August 2014. There were three open-label, dose-escalation groups receiving intravenous doses at Week 0 and Week 4 (5mg/kg, 20mg/kg, 40 mg/kg) and one double-blinded, placebo-controlled group for SC administration (5mg/kg). Cumulatively, 23 participants received 43 doses of VRC01, including five participants who each received two SC 5mg/kg doses. As observed in VRC 601, the IV and/or SC infusions were well tolerated with no SAEs or dose-limiting toxicity [34]. There were only mild local reactions (5/23 participants) limited to redness and tenderness which were more common for the SC dose recipients. Similarly, only mild systemic reactions (nausea, headache, myalgia, malaise) were observed in a minority of participants. Anti-VRC01 antibody responses were not detected, and the mAb retained its expected neutralizing activity in serum.

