  1. Infants should be monitored for a minimum of 4 hours after study treatment injection, with initial assessments at 15, 30 and 60 minutes post dose. Clinic personnel must observe participant for any potential adverse reactions to the study immunization. Equipment, supplies, and properly skilled medical personnel must be immediately available for emergency use in the event of an unexpected adverse reaction.
  2. Infants will also be evaluated for local reactions and pain 1 hour (+/- 30 minutes) after the injection and results recorded on a study CRF.
9. Hematology should include CBC with differential and platelet count. (Not required at screening if collected clinically at birth and results are available).
10. Chemistries should include AST, ALT, total bilirubin, and creatinine. (Not required at screening if collected clinically at birth and ALT results are available).
11. HIV-1 NAT (nucleic acid testing) by a method that detects DNA is required for diagnostic testing since VRC01 might suppress HIV-1 RNA. For the screening NAT, see footnote 12. For U.S. sites, HIV-1 NAT testing must be run in a CLIA-approved laboratory. For non-U.S. sites, the HIV-1 NAT must be run at a VQA-certified laboratory. If the infant has a positive HIV-1 NAT at any time, confirmation and additional samples should be obtained as per APPENDIX IC: HIV-1 Infected Infant Schedule of Evaluations (all dose groups); infant follow up on study should also continue to be as per APPENDIX IB: Infant Schedule of Evaluations (Dose Groups 1 and 2). When possible APPENDIX IC: HIV-1 Infected Infant Schedule of Evaluations (all dose groups) visits should be scheduled to coincide with APPENDIX IB: Infant Schedule of Evaluations (Dose Groups 1 and 2).
12. Blood for HIV-1 NAT drawn at Screening must be obtained prior to 48 hours of life AND prior to VRC01 administration. It may be drawn with the Entry blood. Results may be pending at study entry. If an HIV-1 NAT (DNA or RNA or combined) was collected clinically prior to

48 hours of life and tested in a laboratory with CLIA approval (U.S. sites) or VQA approval (Non-U.S. sites), the test does not need to be duplicated for the study; in this case, results will be abstracted for the study.

13. Lymphocyte subsets include CD3/CD4/CD8 counts and percentages. Results are not needed for study entry. Draw with CBC. Must be performed at CLIA-certified (or equivalent) laboratory.

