## APPENDIX IC: HIV-1 Infected Infant Schedule of Evaluations (all dose groups)

	1 st Visit: Infected Infant (Confirmatory) 	2 nd Visit: Infected Infant 	3 rd Visit: Infected Infant 	Subsequent visits prior to initiation of ARVs  (q28d ±7d)	Follow up after initiation of ARVs 
History 	X	X	X	X	X
Physical exam	X	X	X	X	X
HIV-1 NAT testing 	1 mL 				
Quantitative HIV-1 RNA testing 	3 mL	3 mL	3 mL	3 mL	0 to 3 mL
mAb Plasma levels 	1 mL 	1 mL 	1 mL 		
Lymphocytes: CD3/CD4/CD8 	0 to 2 mL			0 to 2 mL 	0 to 2 mL 
PBMC storage	X 	X 	X 	1 mL	1 mL 
Stored plasma 	X	X	X	X	X
Total Blood Volume Infant (mL)	5-7 mL 	4 mL 	4 mL 	4 – 6 mL 	1 - 6 mL 

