### Footnotes

- Visits for APPENDIX IC: HIV-1 Infected Infant Schedule of Evaluations (all dose groups) should be scheduled to concur with visits for APPENDIX IB: Infant Schedule of Evaluations (Dose Groups 1 and 2), APPENDIX ID: Schedule of Evaluations (Dose Group 3), APPENDIX IE: Schedule of Evaluations (Dose Group 4, Cohort 1: non-breastfeeding), APPENDIX IF: Schedule of Evaluations (Dose Group 4, Cohort 2: breastfeeding), APPENDIX IG: Schedule of Evaluations (Dose Group 5, Cohort 1: non-breastfeeding), or APPENDIX IH: Schedule of Evaluations (Dose Group 5, Cohort 2: breastfeeding) whenever possible. The protocol team will review advance requests for deviations from the specified visit windows on a case-by-case basis.
- The 1st Visit for an Infected Infant (Confirmatory visit) should be as soon as possible after site notification of the first positive result and not later than 14 days after the date of the blood draw of the first positive HIV-1 NAT test.
- The 2nd Visit for an Infected Infant should be 28 days (± 7 days) after the date of the blood draw of the first positive HIV-1 NAT test.
- The 3rd Visit for an Infected Infant Visit should be 56 days (± 10 days) after the date of the blood draw of the first positive HIV-1 NAT test.
- Subsequent visits prior to initiation of ARVs should be every 28 days (± 7 days). Total duration of follow up after study entry should not exceed 48 weeks for Dose Groups 1 and 2 or 96 weeks for Dose Groups 3, 4, and 5.

6. After infant has been started on ARVs, history, physical exam, plasma HIV RNA and CD4 lymphocyte subsets will be abstracted from the medical records when obtained per standard of care. At standard of care clinical visits when blood will be obtained for clinical care, an additional sample for plasma and PBMC storage will be obtained for the study (see LPC). Total duration of follow up after study entry should not exceed 48 weeks for Dose Groups 1 and 2 or 96 weeks for Dose Groups 3, 4, and 5.
7. History should include ARV with start and stop dates, other medications, diagnoses, signs and symptoms, and vaccinations. Results of HIV-1 testing and lymphocyte subset testing done outside of the study should be abstracted.

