10. HIV-1 NAT (nucleic acid testing) by a method that detects DNA is required for diagnostic testing since VRC07-523LS might suppress HIV-1 RNA. For NAT at Screening, see footnote 11. HIV-1 NAT testing must be run in a VQA-approved laboratory. If the infant has a positive HIV-1 NAT at any time, confirmation and additional HIV testing should be performed as per APPENDIX IC: HIV-1 Infected Infant Schedule of Evaluations (all dose groups). Infants confirmed to be HIV-1-infected should be evaluated according to both APPENDIX IH: Schedule of Evaluations (Dose Group 5, Cohort 2: breastfeeding) and APPENDIX IC: HIV-1 Infected Infant Schedule of Evaluations (all dose groups), but without duplication of specific blood tests if the study visit dates are concurrent. When possible, APPENDIX IC: HIV-1 Infected Infant Schedule of Evaluations (all dose groups) visits should be scheduled to coincide with APPENDIX IH: Schedule of Evaluations (Dose Group 5, Cohort 2: breastfeeding).
11. Blood for HIV-1 NAT drawn at Screening must be obtained prior to VRC07-523LS administration. It may be drawn with the Entry blood. Results may be pending at study entry. If an HIV-1 NAT (DNA or RNA or combined) was collected clinically prior to study entry and tested in a laboratory with VQA approval, the test does not need to be duplicated for the study; in this case, results will be abstracted for the study.
12. HIV antibody testing should be performed at the approved site-associated DAIDS-monitored laboratory. If the infant remains antibody positive at or after 72 weeks, notify the protocol team. If HIV antibody is negative at Week 48 or later, subsequent HIV antibody testing is not required.
13. Samples for VRC07-523LS plasma levels should be obtained prior to VRC07-523LS administration. For infants with birth weight <2.6kg use lower sample volume at Entry. Plasma for VRC07-523LS levels and anti-VRC07-523LS levels will be processed and batch shipped per the LPC. Leftover plasma will be stored per the LPC for future HIV-related studies overseen per IMPAACT SOP. See LPC for collection procedure, processing, storage, and shipping instructions.

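### Infants NAT-positive before dosing have no scheduled pre-dose plasma HIV-1 RNA, so their planned change from baseline can start after the antibody has begun to act (minor, exploratory)

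*Protocol*

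**What the plan says.** Protocol Section 8.8 will present, for infected infants, "the changes from baseline to subsequent time points in the amount of HIV provirus in PBMC and plasma HIV-1 RNA". It does not say which sample is the baseline. Section 8.2.3 lists the same measurements as outcomes running from the injection to the end of follow-up. Section 1.2 (Follow-up of infected infants) gives the aim as describing how replicating and integrated virus change once VRC01 has been given.

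The row "Quantitative HIV-1 RNA testing" stands in Appendix IC and in no other infant schedule. The first such test is at the confirmatory visit, which is to follow promptly once the site learns of the positive result and "not later than 14 days after the date of the blood draw of the first positive HIV-1 NAT test". The second "Visit for an Infected Infant should be 28 days (± 7 days) after the date of the blood draw" of that same positive.

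Before dosing, the only scheduled infant virology is the screening NAT. In Appendix IB (Dose Groups 1 and 2), blood for it "must be obtained prior to 48 hours of life AND prior to VRC01 administration", and a study-run test must be "by a method that detects DNA is required for diagnostic testing since VRC01 might suppress HIV-1 RNA". Each of Appendices IB and ID to IH adds of the screening NAT: "Results may be pending at study entry".

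On the course of viremia after antibody, Section 1.1.4 (Clinical Studies) reports that the average load in adults given one 40 mg/kg IV dose of VRC01 was "significantly decreased between days 3 and 21 after infusion compared to baseline, with the nadir at day 9". The drop was 1.1 to 1.8 log10 in 6 of 8 viremic adults not on ART.

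**The concern.** An outcome followed from the injection needs a starting value from before the injection. The plan allows an infant already infected at birth to be dosed before the screening result is known, and it schedules that infant's first RNA quantification only after the result has come back. Read with the schedule, the natural baseline for Section 8.8 is then a post-dose value. The protocol recognises the underlying problem for diagnosis, where it requires a DNA-detecting method because the antibody may suppress RNA, but does not carry it over to its own quantitative analysis.

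At stake is the description of individual RNA courses in a handful of infants. If the first value is already lowered, the change reported from it understates any early fall. With so few infants there is no averaging to dilute one misplaced baseline. No primary or secondary result depends on this.

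**Working it through.** **1. Is any pre-dose blood assigned to quantitative RNA?** Sum the volume rows of each schedule and compare with its stated total.

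- Appendix IC, first visit: NAT 1 + RNA 3 + antibody level 1 + lymphocytes 0-2 = 5-7 mL (stated 5-7 mL, reproduced).
- Screening: IB and ID 1+1+1+1 = 4 mL (stated 4); IE and IF 3-4 mL (stated 3-4); IG and IH 2-3 mL (stated 2-3).
- Entry: IB, ID, IE and IF 2 + 0-1 = 2-3 mL (stated 2-3); IG and IH 2-3 + 0-1 = 2-4 mL (stated 2-4).

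Every total closes without an RNA volume, so none is planned before dosing.

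**2. When is the first RNA value for a screening-positive infant?** Post-dose day = (draw day + lag) − dose day, with a lag of at most 14 days.

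- Dose and draw on the same day: 14 − 0 = day 14.
- Draw at birth, dose at the end of the 72-hour window: 14 − 3 = day 11.
- Draw at birth, dose on Day 5: 14 − 5 = day 9.

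At the limit, the first value therefore falls on post-dose day 11-14 (72-hour groups) or 9-14 (5-day groups). A faster result brings it forward. The second value, 21-35 days after the draw, falls on post-dose day 16 (21 − 5) to 35.

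**3. When is it for infants first positive later?** Earliest = visit day − window; latest = visit day + window + 14. Days count from the birth dose, with the windows of Dose Groups 3-5.

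| First positive visit | First RNA (days) |
|---|---|
| Day 14 ± 3 | 11 to 31 |
| Day 28 ± 3 | 25 to 45 |
| Week 12 ± 1 week (Dose Groups 4 and 5) | 84 − 7 = 77 to 84 + 7 + 14 = 105 |
| Week 24 ± 1 week | 168 − 7 = 161 to 168 + 7 + 14 = 189 |

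Only the screening-positive case, and the early end of the Day 14 case, comes near day 9.

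**4. How much could a late start hide?** This is an illustration on borrowed figures. Assume the adult drop of 1.1-1.8 log10 (10^1.1 = 12.6-fold to 10^1.8 = 63-fold), falling linearly from day 0 to day 9 and returning linearly by day 21 or day 28. The share present at day t is t/9 up to day 9, then (end − t)/(end − 9).

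| First RNA at | Share of drop already present | log10 outside the measured change |
|---|---|---|
| Day 3 | 3/9 = 33% | 0.37 to 0.60 |
| Day 9 | 100% | 1.1 to 1.8 |
| Day 14, return by day 21 | 7/12 = 58% | 0.64 to 1.05 |
| Day 14, return by day 28 | 14/19 = 74% | 0.81 to 1.33 |

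For first values on days 3-14, about 0.4 to 1.8 log10 of an adult-sized drop would lie outside the reported change.

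**5. How many infants?** The documents give no figure for infection at birth in this trial. If 2-5% of the 79 planned infants were infected in total (an assumption), that is 79 × 0.02 = 1.6 to 79 × 0.05 = 4.0. Screening-positive infants are a subset. The breastfeeding groups hold 13 + 10 + 10 = 33 of the 79, and infection there may come later.

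**The case against.** The case against is substantial, and most of it limits the point without removing it.

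- A reader might infer that RNA in every infected infant starts near the antibody's nadir. Step 3 rules that out: infants first positive at Day 28 or later are weeks to months from the birth dose. Dose Group 3 is also re-dosed monthly, so a single nadir does not describe it. Even for screening-positive infants, 14 days is a ceiling.
- A reader might infer that later values will show no fall, or a rise, and that the antibody's effect is missed. The documents do not support this. The adult figures come from a single IV dose of VRC01 without ART, while these infants receive one of three antibodies subcutaneously, with prophylactic antiretrovirals for all and therapy for those infected. RNA may keep falling on antiretrovirals whatever the baseline, and a perfect pre-dose value would still not separate the two effects.
- Section 1.2 says the study is not designed to test viral suppression as a route to cure, and objective 2.3.2 is descriptive. This stands, and sets the severity. But a description of change still needs a stated starting point.
- Partial sources exist: outside HIV results are abstracted, a clinical pre-dose NAT may be an RNA test, and leftover Entry plasma is stored. None is assigned to a baseline RNA. The plasma is kept for future HIV-related studies, whereas Entry PBMC are earmarked for characterizing virus in infected infants.
- The SAP (Sections 1.1 and 2.2) leaves other objectives to separate plans, where baseline might be defined. That is possible, but those plans are not among the documents supplied, and a definition alone would not create a pre-dose measurement.

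**Conclusion.** The point holds for one subgroup: infants whose pre-dose screening NAT is positive and who are dosed before the result is known. Following the schedule as written leaves them with no pre-dose quantitative RNA and a first value as late as post-dose day 9-14, so the Section 8.8 change can begin after the antibody has started to act and may miss part or all of any early fall. How much is unknown: the illustrative 0.4-1.8 log10 rests on carrying the adult IV timing and size over to infants and on an assumed linear course.

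For infants first positive after dosing, the defect is only that baseline is undefined and can lag the first positive draw. Provirus is not affected at sites able to store Entry PBMC. The number of infants concerned may be zero to a few. Severity is minor and confined to an exploratory analysis. It is still more than a missing definition, because no scheduled test supplies the value that the analysis needs.

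**What to change.** In Section 8.8 and Appendix IC:

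- For screening-positive infants, define the RNA baseline as the pre-dose Entry sample and run quantitative RNA on its leftover stored plasma, or use an abstracted clinical pre-dose quantitative RNA.
- Where neither is available, list RNA by days since dose and days since antiretroviral start, and report no change from baseline. Appendix IC already collects antiretroviral start and stop dates.
- For infants first positive after dosing, anchor RNA to the first NAT-positive draw where stored plasma allows, label that value as post-dose, and do not interpret the change as an antibody effect.

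The cost is about one assay per infected infant, with no new visit or draw. There are two drawbacks. Section 9.3 gives only 0.4-1.0 mL of plasma per sample, shared with the antibody-level and anti-drug antibody assays and smaller than a 3 mL draw would yield, so the detection limit will be higher. The stored plasma must also be routed to the site's single qualified RNA laboratory (Appendix IC, footnote 10), whereas plasma for antibody levels is batch-shipped under the LPC.
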